# 12 Study analysis

## 12.1 Sample size calculation

No sample size calculation, proof of concept open label study.

## 12.2 Analysis of the samples

Not applicable (no sample taking)

## 12.3 Statistical analysis

This is a proof of concept open label study that will compare outcome data with a historical control group. Only descriptive analyses will be performed, the sample size will be too low for any meaningful statistical analysis.

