# 6 Introduction

The main causes of benign gastrointestinal (GI) strictures are inflammatory (eg: reflux disease, eosinophilic esophagitis, Crohn's disease, caustic...) or iatrogenic (postirradiation, post endoscopic (sub)mucosal resection, post radiofrequency ablation, anastomotic...). Most strictures respond well to endoscopic balloon dilation. Nonetheless, more than one third of patients develop recurrent symptoms after dilation within the first year (1).

In some case, the stricture can be difficult to treat and require multiple dilation sessions to obtain long-term relief of dysphagia, eating difficulties or lower GI obstructive symptoms (2, 3). A refractory stricture is defined as a cicatricial or fibrotic narrowing luminal diameter resulting in clinical symptoms of a) dysphagia (esophageal strictures), b) gastric outlet obstruction (for strictures of the stomach, pylorus, duodenum of gastrojejunal anastomosis) or c) lower GI obstruction (abdominal distension and cramps, vomiting) with an inability to successfully remediate the anatomic problem to a sufficient diameter over 3 dilation sessions at two-week intervals (4). A recurrent stricture is defined as a cicatricial or fibrotic narrowing with an inability to maintain a satisfactory luminal diameter for four weeks (4). Several options (stenting, intralesional injection of corticosteroids, needle knife incision) have been proposed to manage these strictures, with a varying success rate (5). A significant proportion of patients will finally need self-bougienage or surgery (5).

In conclusion, the treatment of GI strictures remains a challenge for clinicians and there is an unmet need for novel approaches to manage the patients suffering from this condition in order to avoid repeated dilations and/or invasive surgery.

XiapexR is a locally injectable collagenase approved for the management of Dupuytren's and Peyronie's disease (6, 7). Xiapex is a mixture of two collagenases, enzymes produced by the bacterium *Clostridium histolyticum* that dismantle collagen. Approximately 24 hours after local injection, the collagen fibres have lost their

strength and can be easily broken by manipulation. This therapy has been a breakthrough in the management of Dupuytren's disease, avoiding surgery in the vast majority of patients (6).

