## 7.3 The subjects

### 7.3.1 Number of subjects

Active group: 10 patients presenting with refractory GI strictures.

Control group: A historical cohort that consists of 40 consecutive patients that received an endoscopic balloon dilation 12-15mm for a refractory GI stricture at our centre.

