### 7.3.2 Inclusion criteria

The patient is 18-90 years old The patient suffers from a GI stricture The stricture is amenable for endoscopic dilation The patient has undergone at least 1 previous endoscopic dilation for the same stricture within the last 3 months The patient has signed the ICF

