### 7.3.3 Exclusion criteria

The patient is not fluent in Dutch

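### The 10 treated patients and 40 historical controls are compared without recording or showing stricture cause, so a difference in cause mix could create or hide an apparent benefit and would not be visible

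*Combined protocol and SAP*

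**What the plan says.** Section 3 sets a comparative objective: does injection followed by dilation do better than dilation alone? Section 7.1 makes the comparator a historical cohort, and section 9 confirms that nothing is randomised.

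Section 7.3.1 defines the two groups as "Active group: 10 patients presenting with refractory GI strictures" and "A historical cohort that consists of 40 consecutive patients that received an endoscopic balloon dilation 12-15mm for a refractory GI stricture at our centre". Eligibility puts no limit on cause. The relevant inclusion criterion in section 7.3.2 is "The patient suffers from a GI stricture", and the only exclusion in section 7.3.3 is "The patient is not fluent in Dutch".

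Section 6 separates two families of cause: "inflammatory (eg: reflux disease, eosinophilic esophagitis, Crohn's disease, caustic" and others on one side, "iatrogenic (postirradiation, post endoscopic (sub)mucosal resection, post radiofrequency ablation, anastomotic" and others on the other.

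Section 8.1 has the control files reviewed for outcomes and mentions no other item. Section 12.3 says the study "will compare outcome data with a historical control group", adds that the analysis is descriptive only, and says the sample is too small for more. No section plans a baseline table or a breakdown by cause. The only split is by site, upper against lower tract, in section 4. It serves the two symptom scores and not the primary count.

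**The concern.** Without randomisation, nothing in the design makes the two groups alike in cause. The treated patients consent prospectively; the controls are consecutive cases from a period that the protocol does not define. With 10 patients on one side, one or two patients move a class share by 10 or 20 points.

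If some causes need more repeat dilations than others, the crude difference adds a mix effect to any drug effect. A lighter mix in the treated group would look like benefit; a heavier mix would conceal it. Because no test is planned, the side-by-side figures are the result, and they are what a decision on a larger trial would draw on. As the plan stands, a reader could neither see a difference in mix nor judge how much of the contrast it might explain.

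**Working it through.** The plan has no sample size, power or effect figure to reproduce (section 12.1), so the calculations below are illustrations.

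**Inputs from the protocol:** 10 treated and 40 controls (section 7.3.1); two classes of cause, with four examples named in each (section 6).

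**Assumed, because the protocol gives no values:** half of patients in each class; class means of 2 and 4 repeat dilations (difference 2, range 1 to 3); within-class SD 1.5; no drug effect.

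**1. Chance imbalance in mix.** Let X ~ Bin(10, p) and Y ~ Bin(40, p) be the numbers in one class, both groups being drawn from the same population. By exact enumeration of P(|X/10 − Y/40| ≥ gap):

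| Class share p | Gap ≥ 20 points | Gap ≥ 30 points |
|---|---|---|
| 0.2 | 18.4% | 3.9% |
| 0.3 | 25.0% | 7.4% |
| 0.5 | 29.4% | 10.4% |

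These are two-sided. At p = 0.5 the distribution is symmetric, so 29.4% / 2 = 14.7% falls in each direction.

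**2. Shift in the crude difference.** Take 3 of 10 treated and 20 of 40 controls in the harder class.
- Treated mean: 0.3 × 4 + 0.7 × 2 = 2.6.
- Control mean: 0.5 × 4 + 0.5 × 2 = 3.0.
- Difference with no drug effect: −0.4.
- In general the shift is the gap in share times the difference in class means: 0.2 × 1 = 0.2 to 0.2 × 3 = 0.6.
- Reversing the shares reverses the sign and hides a benefit of the same size.

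**3. The shift against sampling error.**
- Given the mix: √[1.5² × (1/10 + 1/40)] = √(2.25 × 0.125) = 0.53.
- Letting the mix vary by chance: total variance is 2.25 + 2² × 0.5 × 0.5 = 3.25, so √(3.25 × 0.125) = 0.64.
- The shift of 0.4 is therefore 0.4 / 0.64 = 0.6 to 0.4 / 0.53 = 0.75 standard errors.
- Chance imbalance in mix contributes 1.00 × 0.125 = 0.125 of the total 0.406, or 31% of the variance of the crude difference.

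**4. What reweighting would do.** The control mean reweighted to the treated mix is 0.3 × 4 + 0.7 × 2 = 2.6, which equals the treated mean.
- Its standard error is √(0.3² × 2.25/20 + 0.7² × 2.25/20) = 0.255, against 1.5/√40 = 0.237 for the crude control mean.
- The treated mean dominates: 1.5/√10 = 0.474.
- The standard error of the contrast is √(0.474² + 0.255²) = 0.54, against 0.53 unweighted.

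**5. How fine a breakdown is workable.** The eight named causes give on average 10/8 = 1.25 treated patients and 40/8 = 5 controls each. Two classes are about the limit for any summary. With 3 and 7 treated patients against 20 controls per class, the within-class differences have standard errors of √(2.25/3 + 2.25/20) = 0.93 and √(2.25/7 + 2.25/20) = 0.66.

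**The case against.** The strongest reply is that section 12.3 already disclaims anything beyond description, and that no test, threshold or decision rule hangs on the difference. That stands to this extent: there is no error rate to inflate, and the issue is how a descriptive contrast will be read. It does not remove the point, since a descriptive difference carries the same mix effect and a table by cause is itself descriptive.

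The second reply is that the premise is not in the documents. No section says re-dilation differs by cause, and section 6 lists causes as background, not as a description of either group. This also stands. A reader might infer support from the reference list, which includes a study of predictors of early recurrence in esophageal strictures. Only its title is visible, and section 6 cites it for how often symptoms recur. Whether cause was a predictor cannot be seen from the documents.

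A reader might also infer that the bias favours the drug, or that the historical design is shown to be confounded by cause. Neither follows. The 29% is ordinary chance imbalance and is two-sided. A systematic difference between the periods is possible, but nothing in the protocol measures it.

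Finally, a reader might conclude that a reweighted control mean should replace the crude one. The exact cancellation in the example depends on two internally uniform classes, whereas the inflammatory class alone pools reflux, eosinophilic, Crohn's and caustic disease. With 10 treated patients and classes this coarse, the choice is debatable.

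The protocol has a better documented mismatch: one previous dilation suffices for inclusion in section 7.3.2, while controls are called refractory, which section 6 defines over three sessions. Those sections need reconciling. That is a separate matter, and settling it would not show the cause mix.

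**Conclusion.** The concern holds as a gap in description and reporting. Followed as written, the plan yields a crude contrast between unrandomised groups in which cause mix can neither be seen nor separated from a drug effect. The protocol is silent on cause; it does not expressly rule out recording it.

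The size is modest and the direction unknown. On the assumptions stated, a plausible imbalance moves the difference by 0.2 to 0.6 dilations either way, with 0.4 as the central illustration, about 0.6 to 0.75 of its standard error. All of this rests on re-dilation differing by cause, on equal class shares, and on assumed means and SD. The documents do not support a claim of demonstrated bias or of false benefit in particular. Handling cause would not make a 10-patient pilot conclusive. The change is still worth making before the control files are reviewed.

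**What to change.** - **Section 8.1:** extract the cause of the stricture from the patient file for both groups, coded as inflammatory or iatrogenic following section 6, with the specific cause also recorded.
- **Section 12.3:** tabulate cause by group. Present the number of repeat dilations within each class beside the crude comparison. List the 10 treated patients individually with cause and outcome.
- **Optional:** show a control mean reweighted to the treated group's cause mix, labelled as a descriptive sensitivity figure. It should not be the basis of the comparison.

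The cost is one extra item from files that are already being reviewed and one table. Within-class figures will be imprecise, and the text should say so. No change to the design, the sample size or patient management is involved.

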# 3 Objective of the study

To investigate whether intralaesional injection with collagenase clostridium histolyticum (XiapexR) into the stricture followed by dilation 24 hours later improves the outcome of patients with refractory gastrointestinal strictures as compared to dilation alone (standard of care).

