### Secondary outcome measures:

1) time to first repeat dilation

- 2) complication rate.
- 3) For upper gastrointestinal strictures only: Dysphagia/gastric outlet obstruction

score (0:, able to eat normal diet; 1: moderate passage: able to eat some solid foods;

2: poor passage: able to eat semi-solid foods only; 3: very poor passage: able to drink liquids only; 4: no oral intake possible

4) For lower gastrointestinal strictures only: (Ileo)colorectal obstruction scoring system (0, requiring continuous decompression; 1, no oral intake; 2, liquid or enteral nutrition; 3, oral intake of soft solids, low-residue diet, or full diet with symptoms of stricture\*; and 4, oral intake of soft solids, low-residue diet, or full diet without symptoms of stricture\*. Symptoms of stricture include abdominal pain/cramps, abdominal distension, nausea, vomiting, constipation, and diarrhea which are related to gastrointestinal transit).

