### 7.3.6 Possible advantages and risks for the subjects

It is possible that participation to the study will result in less need for repeat dilations for a refractory upper GI stricture (unknown).

Every dilation carries the risk of perforation, even in the most experiences hands. No additional dilations are performed in light of the study. It is unknown whether local injection of the study drug augments the risks of perforation. Every patient is carefully monitored after dilation (standard of care). Upon clinical suspicion of perforation, a CT scan is performed for confirmation.

suspicion of perforation, a CT scan is performed for confirmation. In case of confirmed perforation, endoscopic stenting is immediately performed to bridge the defect, allowing healing of the defect. The stent can most of the time be removed after 6 weeks. In some case, endoscopic clipping is the treatment of choice to close the iatrogenic perforation. Surgical intervention is seldomly needed

Side effects of the study drug (XiapexR) are expected to be very limited, as the study drug does not enter the bloodstream in significant amounts and is rapidly degraded in the bloodstream by proteases. Local reactions (bleeding, swelling, inflammation) are theoretically possible. Like all foreign substances, Xiapex can induce allergic reactions but these seem to be very rare (only 1 case described in literature).

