# 8 Procedures

## 8.1 Procedures

After informed consent, patients with an a refractory upper GI stricture will receive a first esophagogastroscopy or ileocolonoscopy with local injection of XiapexR injection into the stricture prior to dilatation. One vial (0.9mg) xiapex in 3ml dissolvent (also provided by the company) will be divided over 4 quadrants within the fibrotic stricture. After 24 hours, a second esophagogastroscopy or ileocolonoscopy will be performed to perform balloon dilation of the stricture 12-15mm (standard of care). The historical cohort will not undergo any procedures, but their patient file will be reviewed to gain outcome data. ICF will be obtained if the patient is still in follow-up at our department.

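### Section 12.3 should add an exploratory effect estimate with its interval and an exact interval for complications; small numbers rule out a confirmatory test, not these

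*Combined protocol and SAP*

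**What the plan says.** Section 3 sets a comparative objective: whether injection followed by dilation "improves the outcome of patients with refractory gastrointestinal strictures as compared to dilation alone (standard of care"). Section 7.3.1 gives 10 active patients and, for control, "A historical cohort that consists of 40 consecutive patients that received an endoscopic balloon dilation 12-15mm for a refractory GI stricture at our centre". The primary outcome (Section 4) is a count, the number of repeat dilations over 6 months. Complication rate is a secondary outcome.

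Section 12.1 gives no sample size calculation. Section 12.3 says outcomes will be compared with the historical group and continues: "Only descriptive analyses will be performed, the sample size will be too low for any meaningful statistical analysis". No section names an effect measure, an interval, or a breakdown of the primary outcome by stricture site.

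On site the protocol is mixed. Section 4 has a separate score "For lower gastrointestinal strictures only: (Ileo)colorectal obstruction scoring system", and the inclusion criteria in 7.3.2 admit any GI stricture amenable to dilation. Section 7.3.6, however, speaks of "less need for repeat dilations for a refractory upper GI stricture (unknown"), and Section 8.1 says "patients with an a refractory upper GI stricture will receive a first esophagogastroscopy or ileocolonoscopy with local injection", which names upper strictures and a lower endoscopy in one sentence.

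**The concern.** The reason given in 12.3 does not reach as far as the restriction it is used for. A small sample is a good reason not to test for efficacy. It is no reason to leave out how large the observed difference is and how uncertain it is.

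The practical risk is two bare summaries offered as the answer to Section 3, or a complication rate of 0% in 10 patients read as reassurance. Section 6 says the drug has never been evaluated in refractory GI strictures, and 7.3.6 says it is unknown whether injection raises the perforation risk. A pilot mainly informs whether and how to run a controlled trial, and that decision needs the uncertainty in view.

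**Working it through.** There is no power or sample size figure in the plan to reproduce. The check is what 10 and 40 patients can show.

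**1. Complications (needs no assumed rate, only example counts).** Exact two-sided 95% limits:
- 0/10: upper limit 1 − 0.025^(1/10) = 0.308, so 0 to 30.8%.
- 1/10: lower limit 1 − 0.975^(1/10) = 0.003; upper limit, the 97.5% point of Beta(2, 9), = 0.445. So 0.3% to 44.5%.
- 0/40, for comparison: 1 − 0.025^(1/40) = 0.088, so 0 to 8.8%.
- A complication with a true rate of 5% (assumed) would be seen at least once in 10 patients with probability 1 − 0.95^10 = 0.40.

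**2. Why omitting a test is reasonable.** In SD units, the SE of a mean difference is √(1/10 + 1/40) = 0.354. At two-sided 5% and 80% power (assumed, normal approximation), the detectable difference is (1.960 + 0.842) × 0.354 = 0.99 SD. Power is 29% at 0.5 SD and 62% at 0.8 SD.

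**3. Why an estimate is still possible.** The 95% half-width is 2.01 × 0.354 = 0.71 SD (t, 48 df). It is wide but computable, and the width is itself the finding.

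**4. The same in dilations.** The documents give no dilation rate, so the following are assumptions: control mean m of 1 to 3 per 6 months, variance/mean φ of 1 to 3, true ratio 0.5. Then SE = √[φ(0.5m/10 + m/40)], and the approximate interval for active minus control is −0.5m ± 1.96 SE:

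| m | φ | SE | Approximate 95% interval |
|---|---|---|---|
| 1 | 1 | √0.075 = 0.274 | −1.04 to 0.04 |
| 1 | 3 | √0.225 = 0.474 | −1.43 to 0.43 |
| 3 | 1 | √0.225 = 0.474 | −2.43 to −0.57 |
| 3 | 3 | √0.675 = 0.822 | −3.11 to 0.11 |

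So even a halving of repeat dilations may or may not be distinguishable from no difference.

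**5. How well a Welch interval behaves.** With simulated gamma-Poisson counts, 10 v 40, control means 1 to 3 and ratios 0.25 to 1, coverage of the nominal 95% interval was about 91% to 96% when the active group was no more dispersed than the controls. It fell to 86% to 92% with variance/mean 3 in the active group against 1 in the controls.

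**6. The awkward case.** If all 10 active counts are equal, for example all zero, the active variance is estimated as 0 and the interval reflects control variation only. At m = 1 and ratio 0.5, all ten are zero with probability e^(−5) = 0.7% (φ = 1) or 3^(−2.5) = 6.4% (φ = 3). At ratio 0.25 these become e^(−2.5) = 8% and 3^(−1.25) = 25%.

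**The case against.** The strongest reply is that 12.3 omits nothing explicitly. It promises a comparison, calls it descriptive, and a description may include a difference and an interval. In a pilot that openly has no sample size calculation, the point is then only a request for more detail. Much of this stands: a reader might infer that the plan forbids estimation, or that it contains a wrong figure, and the documents support neither. But 12.3 does give a reason for limiting the analysis, and that reason does not cover estimation.

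A second objection is that a formal interval against a non-randomised historical group may lend false authority. This also stands, and is why the caveat belongs in the text of 12.3. The entry rules show the problem. Section 7.3.1 calls both groups refractory, yet 7.3.2 asks only that "The patient has undergone at least 1 previous endoscopic dilation for the same stricture within the last 3 months", while Section 6 defines refractory by an "inability to successfully remediate the anatomic problem to a sufficient diameter over 3 dilation sessions at two-week intervals".

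A third is that a ratio suits count data better than a difference. With 10 patients and possibly no events, however, a ratio interval needs ad hoc corrections that can misbehave. One such construction, adding 0.5 to the events with a special rule for zero, gave an upper limit of 1.22 for no active events but 0.95 for one, at a control mean of 1. A simple difference is easier to read and its weaknesses are easier to state.

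Finally, a reader might infer that the unmatched controls call for a site-adjusted model. The documents give no dilation rate by site and no site mix, so any size for that bias would be invented. A listing is what they support.

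**Conclusion.** The point holds as a cheap improvement of minor to moderate weight. Leaving out a confirmatory test is right. Leaving the effect estimate and its uncertainty unspecified is not justified by the reason given.

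The firmest figures are the complication limits (0/10: 0 to 30.8%; 1/10: 0.3% to 44.5%), which assume nothing beyond the example counts. The half-width of 0.71 SD assumes equal SDs in the two groups. The intervals in dilations rest on assumed means and dispersion and show only the order of magnitude.

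An interval will not settle efficacy. It shows sampling error and leaves the historical-control bias untouched. Confidence is medium.

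**What to change.** Replace the restriction in 12.3 with a paragraph such as:

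> As an exploratory, non-randomised comparison with no efficacy test, we will report the number of repeat dilations over 6 months for every active patient and its distribution in controls, and the difference in mean number (active minus control) with a Welch 95% CI. If all active counts are equal, we will state that this interval reflects control variation only. The proportion of patients with at least one complication will be given per group with an exact binomial 95% CI. The primary outcome will be listed by upper or lower stricture site, without subgroup inference. Patients with less than 6 months of follow-up will be listed with the reason. The intervals cover sampling error only and not bias from the historical control, including the difference between entry after at least 1 previous dilation (7.3.2) and refractory controls (7.3.1, as defined in Section 6).

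Add stricture site and follow-up length to the items taken from the historical files; Section 8.1 mentions only outcome data. Reconcile the upper GI wording in 7.3.6 and 8.1 with Section 4 and 7.3.2. If only upper strictures are meant, the site listing falls away.

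The cost is one paragraph, two file-review items and a little analysis. The intervals will be wide, and the Welch interval is approximate, with coverage below nominal if the active group is the more dispersed. Listing patients with short follow-up makes the problem visible but does not correct for it.
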